4.1 Planned Covariates

The relationship of covariates to efficacy endpoints will be explored if appropriate.

4.2 Subgroups

Biomarker data may be incorporated in additional exploratory subgroup or multivariate analyses. The analyses of biomarkers may be performed after collection of all samples during the conduct of the study and therefore may be reported after the primary analysis of efficacy endpoints.

A safety analysis of CRS outcomes will be performed for subjects who were administered siltuximab in order to assess safety amongst subjects who receive siltuximab due to unavailability of tocilizumab for the treatment of CRS.

5. Definitions

5.1 General Definitions

Age at Enrollment

Subject age at enrollment will be determined using the age in years reported in the clinical database.

Investigational Product

The term 'investigational product' is used in reference to AMG 330.

Cumulative Dose of AMG 330

AMG 330: The cumulative dose in microgram (μg) is defined as the following with summation over infusions:

$$\sum (\text{duration of infusion (days)} \text{ for each dose received} \times \text{dose received} [\mu\text{g/day}])$$

Bazett-corrected QT Interval (QTcB)

The Bazett correction will be calculated from the investigator reported QT (msec) and RR interval (msec), as follows: $\text{QTcB} = \text{QT} / (\text{RR}/1000)^{1/2}$.

Fridericia-corrected QT Interval (QTcF)

The Fridericia correction will be calculated from the investigator reported QT (msec) and RR interval (msec), as follows: $\text{QTcF} = \text{QT} / (\text{RR}/1000)^{1/3}$

Derivations of QTcB and QTcF will be performed only when not available.

5.2 Study Points of Reference

Baseline

For any variable, unless otherwise specified, the baseline is the closest value taken prior to, or on the day of, the first administration of AMG 330. For parameters/assessments not scheduled to be performed (or scheduled but not performed) on the same day as the first administration of AMG 330, the baseline value is the value from the screening period measured closest to the day of first administration of AMG 330.

Baseline and Post-baseline ECG Values in Triplicate

The baseline ECG is defined as the mean of all pre-dose assessments; the mean of values in a triplicate should be calculated before taking the mean of the triplicate averages.

For all post-baseline ECG, the mean value for measurements taken at the same assessment will be calculated and used in the analysis.

For pre- and post- dose ECG measurements, unscheduled ECG measurements of a triplicate will be included in the average for a timepoint. Where an ECG is missing within a triplicate, all available data will be averaged for that timepoint.

Change from Baseline

Change from Baseline is the arithmetic difference between post-dose assessments and Baseline value.

Change (absolute) from Baseline = (Post-baseline Value – Baseline Value)

Percent Change from Baseline

Change (percent) from Baseline = [(Post-baseline Value – Baseline Value)/Baseline Value]x100

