e Vital signs will also be assessed prior to subject's discharge from hospital in order to detect possible signs and symptoms of infusion reactions.

f Bone marrow assessment at D8 is optional. Bone marrow assessments on D36 and D43 only if blasts are higher than 5% at prior assessment (see section [6.2.1.1](#) ). For subjects in Group 2, MRD assessment required using both local and central testing. See section [7.5.2](#) for a detailed description.

g In case of extended infusion-free interval, there will be weekly visits at site, assessments will be performed as on D36. In case the infusion-free period between two cycles will only last one week, D36 assessments do not apply and will be replaced by D1 assessments of the following cycle.

i Schedule for ECGs during cycle 1 also applies in case of intra-subject dose escalation.

j If sample processing / shipment is not logistically feasible for a certain time point (eg, in case it coincides with the weekend) this sample time point is not mandatory.

k Day 1 HR1 and HR12 collection only for Group 1 (do not collect for Group 2 or Group 3).

**Table 13. Schedule of Assessments for Cohorts With 28 Day Infusion Duration Treatment Cycle 2 and Following to End of Study**

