**higher, hospitalization is at the discretion of an investigator for all groups.**

Subjects can be hospitalized for a longer time period at the discretion of the investigator. If required for logistical reasons (eg, long travel times), subjects may be hospitalized the day before dosing (day -1) of any cycle and at the EOI for cycle 1 for required PK samples.

See Section [6.2.1.1](#) for duration of infusion cycles and infusion-free interval.

In the second week of cycle 1, subjects will return to the clinic for two visits. In case of 21- or 28-day treatment cycles twice weekly visits at the clinic will also be required in the third and fourth week (as applicable) week of infusion. Weekly visits will apply during the infusion-free interval.

Treatment begins on day 1 (cycle 1 day 1) when the first cIV infusion of investigational product is administered to a subject.

The following procedures will be completed during the treatment period at the times designated in the Schedules of Assessments ([Table 8 – Table 23](#)).

**Note:** After each dose step, the assessments described in [Table 14](#) have to be performed.

Investigational product is to be administered after all other protocol-required pre-dose assessments have been performed on D1 of each cycle.

The results of the D1 laboratory tests taken prior to infusion start will not have to be available before starting treatment with AMG 330. Laboratory assessments that were done within 24 hours prior to treatment start do not need to be repeated at D1 prior to infusion.

- Hospitalization
- Clinical evaluation
  - Physical examination as per standard of care. Physical examination findings should be recorded on the appropriate eCRF
  - ECOG performance status
  - Weight
- Vital signs (ie, blood pressure, heart rate, respiratory rate, and temperature)
- Pulse oximetry
- ECG triplicate measurement
- Laboratory assessments: hematology, chemistry, coagulation, urinalysis, and serum pregnancy test (females only)

- Biomarker assessments: [REDACTED], immune cell subsets and markers of immune system activation, MRD, LSCs, tumor mutation and phenotype analysis, and serum and plasma marker analysis
- AMG 330 PK sample collection
- Anti-AMG 330 antibody sample collection
- Bone marrow aspirate / biopsy
- Serious adverse event reporting
- Adverse event reporting
- Disease-related event reporting
- Documentation of concomitant and rescue medications

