### 7.3.8        **Electrocardiogram Performed in Triplicate**

The subject must be in supine position in a rested and calm state for at least 5 minutes before ECG assessment is conducted. If the subject is unable to be in the supine position, the subject should be in most recumbent position as possible.

Electrocardiograms should be performed in a standardized method, in triplicate, and approximately 30 seconds apart, prior to blood draws or other invasive procedures. Each ECG must include the following measurements: QRS, QT, QTc, RR, and PR intervals.

Electrocardiograms will be performed as follows:

- Three baseline ECGs will be collected  $\geq$  30 minutes apart, with each baseline ECG in triplicate run consecutively (ie, < 30 seconds apart; 2 sets collected at screening, and 1 set collected pre-dose on day 1 [ie, total  $\geq$  9 ECGs])
- Triplicate ECGs at time points after dosing

Baseline is defined as predose assessments from cycle 1 day 1. The investigator or designated site physician will review all ECGs. Electrocardiograms will be transferred electronically to an ECG central reader for analysis per Amgen instructions. Once signed, the original ECG tracing will be retained with the subject's source documents. At the request of the sponsor, a copy of the original ECG will be made available to Amgen. Standard ECG machines should be used for all study-related ECG requirements.

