**Rationale:**

The protocol was amended following comments received by the FDA on May 12th, 2015 and on May 15th, 2015, and in line with the responses to questions submitted to the IND on May 19th, 2015.

The following changes were implemented as requested by the FDA:

- specific recommendations for infection prophylaxis (neutropenic subjects) as well as description of mitigation measures for cytokine release syndrome and tumor lysis syndrome, and provisions for identifying subjects at high risk of cytokine release syndrome and tumor lysis syndrome were added.
- implementation of possibility for DLRM to introduce steroid pre-treatment for subsequent cohorts in case of observation of cytokine release syndrome
- addition of recommendation for 9 days of hospitalization in first treatment cycle
- DLT criteria were updated as per FDA request
- rolling 6 design was replaced with 3+3 design
- the dose escalation scheme was modified in accordance with FDA requests for slower escalation in the first dose cohorts.
- a waiting period prior to dosing of the next subject was implemented for the first 10 subjects receiving step dosing (if applicable)
- an additional time point for coagulation and hematology safety labs was added (8 h post treatment start in the first cycle and after step if applicable)
- the subject population that should receive pre-treatment with hydroxyurea prior to start of AMG 330 treatment was specified

---

In addition to changes requested by the FDA, the following administrative changes were made:

- change of US study manager
- adverse event CRF was replaced with event CRF following current DES standards
- list of analytes for chemistry and hematology were updated to reflect eCRF contents

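### The general baseline rule in SAP 5.2 has no pre-dose condition, so a day 1 post-dose safety lab can become baseline when the pre-dose draw is waived

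*SAP*

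**What the plan says.** SAP 5.2 sets one default for all variables: "the baseline is the closest value taken prior to, or on the day of, the first administration of AMG 330". A fallback to the screening value applies to assessments "not scheduled to be performed (or scheduled but not performed) on the same day as the first administration of AMG 330". SAP 5.3 defines Study Day 1 as a calendar day, not a clock time.

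ECG is handled separately and restricted to values before dosing: "The baseline ECG is defined as the mean of all pre-dose assessments". The protocol also has a pre-dose sentence, "Baseline is defined as predose assessments from cycle 1 day 1", but it stands in the ECG section (7.3.8). I found no equivalent for labs, vital signs or biomarkers.

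Protocol 7.2.2 contains a waiver: "Laboratory assessments that were done within 24 hours prior to treatment start do not need to be repeated at D1 prior to infusion". The cycle 1 schedules (Protocol Tables 8, 10 and 12) show one hematology, chemistry and coagulation draw in the hours after the infusion starts on day 1. The amendment history describes the added coagulation and hematology time point as "8 h post treatment start in the first cycle". The same tables schedule repeated vital signs, serum markers and immune cells after the start on day 1.

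SAP 9.6.4 and 9.6.5 then allow, without requiring, change-from-baseline summaries for labs and vital signs and maximum-shift tables for selected labs.

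**The concern.** A baseline should describe the subject before exposure. Here the wording admits values from the dosing date in addition to values before dosing, and day 1 carries many samples taken after the infusion has begun. Including a pre-dose condition for ECG and omitting it from the default leaves a programmer free to apply the default literally.

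Day 1 values after the start are a poor reference. Protocol 2.3 (Table 2) lists cytokine release syndrome as an identified risk, with tachycardia, hypotension and transaminase elevation among its signs. Protocol 6.6 places increased risk in the first few days. Outside the separate instructions for Groups 4 and 5, dexamethasone is given within an hour of the start (Protocol 6.3). A value taken hours later may already contain drug or steroid effect, and that early movement would drop out of any change measured from it.

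**Working it through.** No sample size, power or error rate depends on this rule, so there is no planned figure to reproduce. The check is whether a site that follows the protocol can generate a post-dose baseline.

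**Inputs.** The default and fallback (SAP 5.2); the 24-hour waiver (Protocol 7.2.2); one post-start safety-lab draw on day 1 (Protocol Tables 8, 10, 12). I take the draw at 8 h, the hour in the amendment history. Column alignment in the tables is not fully secure in the text copy, so I also show 6 h.

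1. **Is the post-dose draw on the dosing date?** A sample h hours after the start keeps that date if the infusion starts before 24 − h. For h = 8: 24 − 8 = 16, so a start before 16:00. For h = 6: before 18:00. For h = 12: before 12:00.

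2. **Which lab is closest when the day 1 pre-dose draw is waived?** Let t be the hours from the last pre-dose lab to the start, with t at most 24, and let the start be before 16:00.
   - By clock time, the 8 h draw is closer when t > 8. That is (24 − 8)/24 = 2/3 of the permitted window. This is a share of the window, not of subjects.
   - By date, the 8 h draw is the only value dated day 1 whenever the pre-dose lab carries the previous date. Protocol 6.2.1.1 and 7.2.2 allow admission on day −1, so this is realistic.
   - If the pre-dose lab was taken earlier on day 1, the two values tie by date and the SAP gives no tie-break.

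3. **Does the fallback rescue the case?** It applies when the assessment was not performed on the dosing day. The pre-dose draw was not performed, but a draw of the same analytes was. The text can be read either way.

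4. **Other variables.** Vital signs, serum markers and immune cells have scheduled pre-dose slots that the waiver does not cover. A pre-dose value taken shortly before the start is the closest by clock time. A post-dose baseline then needs a missed pre-dose sample (a footnote to Table 12 makes biomarker time points non-mandatory when processing or shipment is not feasible) or a derivation by date alone, where same-day values tie.

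5. **Effect on a reported change.** Let D be the true change to the later extreme, d the change already present in the post-dose sample, and f = d/D. The reported change is D − d, so the share retained is 1 − f. The documents give no early-change data, so f is assumed:

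| f | Share of true change reported |
|---|---|
| 0.10 | 90% |
| 0.25 | 75% |
| 0.50 | 50% |
| 1.00 | 0% |
| −0.25 | 125% |
| −0.50 | 150% |

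Early movement in the same direction as the later extreme shrinks the change; movement in the opposite direction inflates it.

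**The case against.** The best defence is that the intent is plainly pre-dose. SAP 5.2 says that "Change from Baseline is the arithmetic difference between post-dose assessments and Baseline value", which sets post-dose values apart from baseline. Protocol 7.2.2 has dosing follow the required pre-dose assessments, and Protocol 7.2 requires exact blood-collection times. The rule also picks the closest value, so a timed pre-dose sample on day 1 will usually win. This shows what was meant, but it does not close the waiver route, where no day 1 pre-dose lab exists.

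Several stronger readings are tempting, and the documents do not support them:

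- A reader might infer that any day 1 value can serve as baseline. The rule says closest, not any.
- A reader might infer that every subject using the waiver is affected. A lab taken earlier on day 1, a lab taken less than 8 h before the start (by clock time), or an infusion starting after 16:00 can each leave the pre-dose value as baseline.
- A reader might carry the waiver over to cytokines, immune cells and vital signs. Protocol 7.2.2 lists its laboratory assessments as hematology, chemistry, coagulation, urinalysis and pregnancy test, separately from vital signs and biomarkers.
- A reader might infer that effects always shrink. Nothing in the documents fixes the direction.

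It is also true that the consequence is limited. The lab and vital-sign summaries are optional, individual labs are still listed and reviewed for dose-level meetings, and biomarker changes are exploratory.

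**Conclusion.** The concern holds in a limited form. The default rule can, under protocol-compliant conduct, make a post-dose hematology, chemistry or coagulation value the baseline when the pre-dose draw is waived and the last pre-dose lab is dated the day before or lies further from the start than the post-dose draw. For other variables it needs a missed pre-dose sample or a date-only derivation.

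The possible distortion runs in either direction. It is confined to the optional lab and vital-sign change and maximum-shift summaries and to exploratory biomarker changes. ECG has its own pre-dose rule. Adverse event grades and DLT status, which form the primary endpoint, do not use this baseline.

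The number of subjects affected and the size of the distortion cannot be computed from the documents. The conclusion assumes a post-start lab draw at about 8 h on the dosing date, pre-dose day 1 samples, where taken, close to the start, and a literal reading of the default. It is worth correcting because the rule as stated can give a wrong result and the correction is nearly free.

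**What to change.** Amend SAP 5.2 as follows:

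- Baseline is the last non-missing value with a date and time before the start of the first AMG 330 infusion.
- A same-day value without a time is accepted only if it is labelled pre-dose; otherwise the latest earlier value is used.
- All day 1 values after the infusion start are post-baseline.
- For Groups 4 and 5, state whether baseline must also precede the first premedication. Footnotes to Protocol Tables 15, 17 and 21 start event recording on day −1 or day −2 when premedication is given then, and SAP 5.4 dates treatment-emergence from whichever product came first, while baseline refers to AMG 330 alone.
- Keep the existing ECG rule.

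The cost is a few SAP sentences and the matching derivation code. Exact blood-collection times (Protocol 7.2) and infusion start date and time (Protocol 6.2.1.1) are already recorded, so no new data or visits are needed.

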5.3 Study Dates

Informed Consent Date

The date on which the subject signs the informed consent form.

Enrollment Date

Enrollment date is defined as the date collected on the Subject Enrollment CRF page.

Study Day 1

Study Day 1 is defined as the first day that AMG 330 is administered to the subject.

Study Day

If date is on or after first administration of AMG 330: study day= (date - date of Study Day 1) + 1

If date is prior to date of first administration of AMG 330: study day= (date – date of Study Day 1)

Last Investigational Product Dose Date

The last IP dose date for each subject is defined as the end date of last infusion of AMG330.

End of Investigational Product (IP) Administration Date

End of IP Administration for each subject is defined as the date of decision was made to end IP reported on the End of IP Administration CRF page.

End of study (EOS)

End of study for an individual subject is defined as the date of the final study visit (EOS visit) when assessments and procedures are performed. The EOS visit should occur approximately 4 weeks (+ 1 week) after the last dose of AMG 330 or prior to the initiation of other AML therapy, whichever occurs earlier. Subjects who complete the EOS visit will be considered to have completed the study.

Death Date

For subjects who die during the study, the death date will be recorded on the end of study CRF in the “date subject ended study” field. Incomplete death dates where only the day of death date is missing will be imputed using the following rules:

Day 1 of the month will be used if year and month indicate that death happened in different month from last known alive date;

One day after last known alive date will be used if death happened in the same month as last known alive date.

The imputed death date will be used in calculation of duration of response, progression-free survival and overall survival.

Last Known Alive Date

For subjects not known to have died, their last date known to be alive will be determined as the latest date associated with clinic visits before data cutoff date including, for example, but not limited to the following:

- Date of Enrollment on Subject Enrollment CRF
- Date First Taken, Date Last Taken on Concomitant Medications CRF
- Date Performed on ECOG Performance Status, Vital Signs, Electrocardiogram, Procedures CRFs
- Admission Date, Discharge Date on Hospitalizations CRF
- Date of Examination on Physical Measurement CRF
- Date Collected on Reproductive Status and Pregnancy Test (Local Lab), Chemistry (Local Lab), Hematology (Local Lab), Coagulation (Local Lab), Urinalysis (local Lab), Immunology (Local lab) CRFs and in central lab data
- Date of Assessment on revised IWG response criteria or modified IWG response criteria for Time Point in CRFs
- Start Date and End Date on Investigational Product Administration CRF
- Date Started and Date Ended or Resulted in Death on Events CRF
- Start date, stop date on Anti-Cancer Therapies, Other Protocol Required Therapy, Other Protocol Required Therapy (██████████, Dexamethasone), Hematopoietic Stem Cell Transplantation Autologous, Hematopoietic Stem Cell Transplantation Allogenic CRFs
- Subject Status Date if status is Alive on Survival Status CRF
- End_of study date if the subject's primary reason for ending study is not “Lost to follow-up”.

5.4 Endpoints

Treatment-Emergent Adverse Event (TEAE)

Events categorized as Adverse Events (AEs) starting on or after first dose of investigational product as determined by "Did event start before first dose of investigational product (enter response based on earliest administration of [REDACTED]
[REDACTED], or AMG330, whichever occurred first)" equal to "No" or missing on the Events eCRF and up to 30 days after last administration of AMG330 or end of study date, whichever is earlier. Disease related events (DREs) will be included in the TEAE summary.

The severity of each adverse event will be graded using the CTCAE version 4.0. Adverse events will be coded using MedDRA. For CRS events, revised grading system will be used as per protocol ([Lee et al. 2014](#)).

Treatment-Related AE

A treatment-related AE is any treatment-emergent AE that per investigator review has a reasonable possibility of being caused by the investigational product.

Dose Limiting Toxicities (DLT)

DLT will be determined by "Is this event a Dose Limiting Toxicity (DLT)?" equal to "Yes" on the Events eCRF. Investigators will determine whether an adverse event qualifies as a DLT per protocol [Section 6.2.1.4](#).

Overall Response:

Overall response definitions are given below for different indications.

Group 1 in dose-escalation cohort / Group 4 (R/R AML)

Response is defined as any of the following:

Complete remission (CR), CR with incomplete recovery (CRI) or morphologic leukemia-free state (MLFS) (all according to Revised International Working Group [IWG] response criteria for AML), or CR with partial hematologic recovery (CRh).

Group 2 (MRD+ AML) (Primary)

Response is defined as CR without minimal residual disease (CRMRD-) or CRI without minimal residual disease (CRiMRD-). MRD- is defined as MRD threshold below 0.1% as per ELN recommendations ([Schuurhuis et al., 2018](#)).

Group 2 (MRD+ AML) (Exploratory)

Group 3 (MDS)

Response is defined as any of the following:

CR or marrow CR (all according to Revised IWG response criteria for MDS)

Group 5 and Group 1 in dose-expansion cohort (R/R AML)

Response is defined as any of the following: CRMRD-, CR, CRi, CRh, MLFS, PR.

Minimum Residual Disease (MRD) Response (All groups):

Minimum residual disease response is defined as MRD negative, indicating presence of leukemia cells to 0.1% or lower of white blood cells.

Duration of Response (DOR):

Duration of response is defined as the interval from the date of the first disease assessment indicating an overall response to the first documented relapse, disease progression, or death due to any cause, whichever occurs first. Subjects without relapse, disease progression or death until the analysis data cut-off date will be censored at the last adequate disease assessment date. Only subjects with a response will be evaluated for DOR.

DOR time in days = earlier of (date of first relapse or disease progression or death or date of censoring) – date of the first observation of overall response +1.

DOR time in months= earlier of (date of first relapse or disease progression or death or date of censoring) – (date of the first observation of overall response +1)/30.4

Overall Survival (OS)

Overall survival is defined as the time from enrollment until death due to any cause.

Subjects alive will be censored at the last known date. If the date last known to be alive is after the date that triggers the analysis (ie, the data cutoff date), the subject will be censored at the date of last contact through the analysis trigger date.

Event-free Survival:

Event-free survival (EFS) is defined as the interval from first administration of AMG 330 to the earliest of date of treatment failure, relapse for responders, or death due to any cause. Censoring is at the last evaluable post-baseline response assessment; otherwise,

at first administration of AMG330. For non-responders, the event date for treatment failure is assigned as the date of first administration of AMG 330.

Event-free Survival in days = earlier of (date of treatment failure or relapse or death or date of censoring) – date of the first administration of AMG 330 +1.

Event-free Survival in months = earlier of (date of treatment failure or relapse or death or date of censoring) – (date of the first administration of AMG 330 +1)/30.4.

Time to Response (TTR)

Time to response defined as the interval from the first administration of AMG 330 to the first documentation of response. Time to response is evaluated only for subjects who achieved a response.

Time to response is calculated as the number of days:

(date of first response – date of study day 1 +1).

6. Analysis Sets

The analysis of all endpoints, unless noted otherwise, will be conducted on the Safety analysis set defined in [Section 6.1](#).

